- a. ECG: The neonate will be stabilized after birth and then will receive a screening 12-lead ECG to rule out QTc Bazett greater than or equal to 480ms. Once the neonate is medically stable and a normal QTc confirmed by the treating physician, the neonate will receive the same 'blinded' study drug (ondansetron or placebo) as his or her mother; this first dose of study drug is to be given between 4-8 hours after delivery. A repeat 12-lead ECG will be done on all neonates following each of the 5 doses of study drug, between 2-5 hours after each dose of study drug. Any neonate that shows significant ECG changes will be excluded from further dosing of study medication but will continue safety follow-up.
 - i. If the QTc is prolonged, the neonate will be transferred to the NICU for continuous cardiac monitoring, if the standard of care indicates the neonate should be admitted to NICU; this will be determined on a case-by-case basis at each site. In addition, a blood test to check the potassium, magnesium, calcium, and ionized calcium levels will be done if the clinical team believe it is necessary for the neonates safety; if the levels are abnormal, electrolytes will be normalized using IV or oral supplements as indicated per standard of care.
 - ii. All ECGs, from all sites, will be sent to Stanford to be interpreted by a cardiologist, who is not a member of the study team, to confirm the accuracy, and consistency of the initial readings.
- b. Standard of Care for Well Baby Nursery:
 - i. Vital Signs: heart rate (HR), respiratory rate (RR), and temperature will be monitored every 4-8 hours depending on the infant's history, and blood pressure at least once per day.
 1. If the HR is less than 80 beats per minute, a rhythm strip or 12-lead ECG is ordered to evaluate the QTc interval, a Neonatal Intensive Care Unit (NICU) physician will assess the neonate and a blood pressure will be obtained.
 2. If the QTc is prolonged, see "ECG" above which discusses the possibility of the neonate being transferred to the NICU for continuous cardiac monitoring if deemed necessary by standard of care
 - ii. A member of the study team will visit the Well Baby Nursery at least once per day to ensure the neonate is doing well and that everyone on the clinical team understands the protocol and knows how to contact the principal investigator to answer questions as needed.

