2.1.2 Inclusion/Exclusion

Criteria

Subjects	Inclusion Criteria	Exclusion Criteria
Maternal/Paternal	Women of reproductive age (18-45 years old, inclusive) and their fetuses/neonates. Daily opioid use for at least 3 weeks prior to delivery Gestational age of \geq 37 weeks to < 42 weeks at delivery. Competent mother willing to sign the informed consent for herself and both parents competent and willing to sign consent/permission for their neonate.	Any condition that, in the opinion of the investigator, would compromise the health of the participant (both mother and fetus) or the integrity of the data. Known allergy to the study medication. Screening 12-lead ECG, if done, showing prolonged QTc will stop the mother from receiving any study drug but her neonate can still be included in the study. Maternal ingestion or administration of ondansetron within 24 hours prior to delivery, for reasons other than study purposes, will exclude the mother and neonate.
Neonatal	Participating mother Maternal (and paternal if	QTcB greater than or equal to 480ms on any 12-lead

	present and competent) consent	ECG post delivery will stop the dosing of the study drug, but safety follow up will be done including blood samples & 12-lead ECG(s) if the mother or baby received at least one dose of study drug.
--	-----------------------------------	---

This study will include special classes of participants: pregnant women and their newborns. The focus of this study is specific to these sensitive populations of pregnant women and neonates and as such warrants their inclusion. We feel that, in balance, the potential for significant benefit to the neonatal population in this study and in future patients outweighs the risks (section 5.0 *Potential Risks* below).

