To Neonate Risk is no greater than placebo risk To minimize risk, screen for QT prolongation and give dose (determined in Aim 1) to reach blood level predicted to have desired clinical effect Dose will be within dose limits studied in slightly older infants (less than 0.15 mg/hr in 12hours) Duration of exposure will be minimized by stopping study drug after a maximum of five days of study drug treatment, Will be discontinued if related adverse events occur If QTc interval abnormalities occur or a neonate has QTcB greater than or equal to 480 ms, the neonate's study drug will be stopped and no further dosing will occur; follow up 'safety' EKGs will be done until the QTc has returned to 479ms or less, if possible. All neonates will have a screening ECG prior to their first dose of study medication & an ECG after each dose for a maximum of 6 ECGs in 5 days.
Delayed onset of NAS
To Mother Not applicable
To Fetus Risk will be managed by educating the parents about the NAS symptoms Provide parents with contact information for both their clinical caregivers and the research team Ask parents to report delayed onset to both groups Appropriate medical care will be provided Parents may receive a maximum of 10 daily follow-up telephone calls if the baby is discharged before Day 15 of life; the calls are being done to review continuation or recurrence of NAS symptoms and the occurrence of other adverse events. The research staff will call daily, through a maximum of 10 days after the last dose of study drug. If the baby is still in the hospital through Day 15 of life, this information will be gathered by the research staff visiting the neonate in the hospital. The final follow-up phone call to the parents will occur approximately 30 days after the baby's last dose of study medication to check for any occurrence of new adverse events and to inquire about the resolution of any previously reported adverse events.
To Neonate Not applicable
Phlebotomy
To Mother Minimize risks of hematoma and infection by following all hospital guidelines including using aseptic technique and applying pressure to site after sample collection Only qualified personnel may collect blood samples for analysis
To Fetus Not applicable

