The null hypothesis for the Fisher's Exact test was that the need for morphine treatment and study drug allocation were independent. The continuous outcomes of secondary endpoints were examined using the two-sided Wilcoxon Rank-Sum test (equivalent to the Mann-Whitney test), where the null hypothesis is stated as the outcomes in the ondansetron and placebo arms are equal. Inclusion of neonates in the safety population was based upon receipt of ondansetron in any form (study drug administered to infant or exposure through maternal transfer). QTc values in the safety population were analyzed by two sample t-test to determine if the mean QTc of two groups were equal. All tests were two-sided, and the p-values obtained from statistical tests were compared with the significance level ($\alpha =0.05$) to determine whether null hypothesis could be rejected or retained. Statistical analyses were performed using R software (version 3.6.1).

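### The SAP compares only mean QTc between arms; no comparison by arm is planned for QTcB at or above 480 ms, the threshold at which the protocol stops dosing.

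*SAP*

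**What the plan says.** **SAP (QTc sentence).** "QTc values in the safety population were analyzed by two sample t-test to determine if the mean QTc of two groups were equal". The SAP's tests are all two-sided, with each null hypothesis rejected or retained at 0.05. The SAP names no ECG (first, last, all), no per-infant summary (mean, maximum, change from screening) and no correction formula. Fisher's exact test is assigned to morphine and to adjunctive therapy, not to any ECG outcome.

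**Protocol 2.1.2.** The neonatal dosing-stop rule is "QTcB greater than or equal to 480ms on any 12-lead" ECG after delivery.

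**Protocol 6.2, risk to the neonate.** On a crossing, "the neonate's study drug will be stopped and no further dosing will occur". Follow-up safety ECGs then run until the value is back to 479 ms or lower, where possible.

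**Protocol 2.1.1, Safety Monitoring.** A screening ECG comes before the first dose. "A repeat 12-lead ECG will be done on all neonates following each of the 5 doses of study drug", so an infant has at most six scheduled ECGs. Also: "Any neonate that shows significant ECG changes will be excluded from further dosing of study medication but will continue safety follow-up".

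**Protocol 2.1.1, Interim Analysis.** The DSMB reviews all ECG measurements from the first 20 pairs. No statistic, arm comparison or threshold count is named.

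**Protocol 9.0.** The neonate's exposure to ondansetron is named as the foremost risk concern.

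**The concern.** Conduct and analysis look at different things. At the cot side the question is whether an infant reaches 480 ms. In the SAP it is whether two averages differ. A test of means, read as retained at 0.05, could be reported as no QTc effect without anyone tabulating how many infants per arm had the drug stopped for QTc.

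The stopping rule also affects the data. Scheduled repeat ECGs are tied to doses, so an infant whose dosing stops contributes no later post-dose ECG. If the t-test uses a later post-dose ECG, the infants with the clearest prolongation are missing from it, and more of them are missing from the arm that prolongs QTc. The SAP does not say whether the safety ECGs after a stop would enter the test.

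**Working it through.** The documents give no QTc mean, SD, crossing rate or power, so there is no planned figure to reproduce. What follows is an illustration.

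**Inputs.** From the documents: 45 infants per arm (SAP), five post-dose ECGs, stop at the first value of 480 ms or more, two-sided 0.05. Assumed: mean QTcB 430 ms, between-infant SD 20, within-infant SD 15. Scenario A: 10% of ondansetron infants are prolonged by 50 ms. Scenario B: all are prolonged by 10 ms.

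**Step 1: one ECG.** SD of a single value = √(20² + 15²) = 25 ms. An unaffected infant crosses with probability P(Z ≥ (480 − 430)/25) = P(Z ≥ 2) ≈ 2.3% per ECG. An infant prolonged by 50 ms crosses with probability P(Z ≥ 0) = 50%. Affected infants therefore leave the dose-linked series quickly.

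**Step 2: true mean difference in A.** 0.10 × 50 = 5.0 ms.

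**Step 3: power of the t-test on the mean of five ECGs, no stop (normal approximation).** Placebo variance = 20² + 15²/5 = 445.
- A: ondansetron variance = 445 + 0.1 × 0.9 × 50² = 670. SE = √((445 + 670)/45) = 4.98. Power ≈ P(Z > 1.96 − 5.0/4.98) ≈ 17%; simulation gives 15%.
- B: SE = √(2 × 445/45) = 4.45. Power ≈ P(Z > 1.96 − 10/4.45) ≈ 61%; simulation gives about 60%.

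**Step 4: simulation with the stop (4,000 replicates).**

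| Quantity | A: 10% +50 ms | B: all +10 ms |
|---|---|---|
| Ever ≥ 480 ms, placebo v ondansetron | about 7% v 14.5% | 7.3% v 15.7% |
| Dose-5 difference, no stop | 5.0 ms | 10.0 ms |
| Dose-5 difference, infants still dosed | 0.8 ms | 7.8 ms |
| t-test power, per-infant means | 15% | about 60% |
| Fisher power on crossings | about 10% | 15% |

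In A, the t-test at dose 5 among infants still dosed rejects in 5% of runs, which is the null rate. At dose 1 the difference is 5.0 ms, undiluted. With each infant's ECGs averaged up to and including the stopping one it is 5.3 ms, also undiluted.

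**Step 5: other assumptions (mean 420 ms, same SDs, 1,500 runs).**
- 10% shifted by 60 ms: crossings 2.5% v 10.1%; dose-5 difference 6.1 ms falls to 1.1 ms.
- 20% shifted by 60 ms: crossings 2.5% v 17.6%; 12.4 ms falls to 2.9 ms. The t-test on full per-infant means and Fisher's test each have 55% power.
- No effect, all ECGs pooled as if independent: the t-test rejects in 29% of runs. The unit of analysis therefore matters as well.

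**Step 6: precision of a count.** With 0 of 45 crossings, the two-sided exact 95% upper limit is 1 − 0.025^(1/45) = 7.9%. At 45 per arm, 6 v 0 is the smallest split against zero that gives p ≤ 0.05.

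**The case against.** The strongest reply has four parts.

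**The mean test may be the better detector.** This stands. In both main scenarios Fisher's test on crossings has less power than the t-test on per-infant means. A reader might infer that the SAP chose an insensitive test and that a test of crossings would detect more; the figures do not support that.

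**The dilution depends on an unstated choice.** This also stands. A reader might infer that the stopping rule biases the comparison whichever scheduled ECG is taken. It does not: no post-dose crossing has removed anyone by the first post-dose ECG, and per-infant averages up to the stop are not attenuated. The bias is conditional on a later post-dose ECG being used.

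**Infants who cross are not lost.** Correct. Protocol 2.1.1, 2.1.2 and 6.2 all keep them in safety follow-up with further ECGs. Only the dose-linked series ends, and the crossings remain countable.

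**The DSMB sees the ECGs.** It reviews them for the first 20 pairs, and under section 9.0 it meets every six months, receives adverse-event frequencies and may unblind. That protects participants during the trial, but no passage commits anyone to a comparison of crossings by arm in the final analysis.

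The documents also use 480 ms as a screening and dosing-stop threshold and never call it a safety endpoint. The point needs no such label: it is the ECG value on which the protocol acts.

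**Conclusion.** The point holds in a limited form. The SAP's one stated QTc analysis tests means, leaves the ECG and per-infant summary open, and omits a comparison by arm of the event that stops dosing. A non-significant result would not show that ondansetron leaves the frequency of that event unchanged.

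Attenuation is a risk only if later post-dose ECGs are used. In the worst case shown, at dose 5, it turns 5.0 ms into 0.8 ms; at dose 1 it is nil. These sizes rest on assumed means, SDs and shifts. The missing comparison of crossings rests on the text alone.

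A reader might go further and infer that the trial cannot answer its main safety concern. The documents do not support that: the ECGs are collected, and an outside cardiologist confirms the readings. What is missing is a planned summary. It should be added, and the reason is estimation of the relevant event, not power.

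**What to change.** 1. Report per arm the number and proportion of infants with any post-dose QTcB of 480 ms or more, with the risk difference and an exact 95% confidence interval.
2. Show screening-ECG crossings separately, since that ECG follows maternal dosing.
3. Add each infant's maximum QTcB up to and including the ECG that stopped dosing.
4. Keep the mean comparison, but state the correction formula and base it on one value per infant that includes the stopping ECG, not on a late-dose ECG among infants still dosed. Say whether safety ECGs after a stop are used.
5. Do not claim absence of a QTc effect from the p-value of the mean test.

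The denominators need one safety population. The SAP gives two definitions, at least one dose of study medication and receipt of ondansetron in any form; the second, read literally, leaves no placebo group. They must be reconciled.

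Cost: SAP wording and one extra table from data already collected. If crossings are few the interval will be wide: zero in 45 infants still allows a rate of up to 7.9%, and the table should show that. No dosing or clinical rule changes.
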